12.13.3. Study Design

This is a multicenter sub-study of the main ASCEND-ND study. Subjects who qualify for the main study will be assessed for enrolment. Approximately 136 subjects from centers in selected countries that are participating in the main study will be randomized. [Note: recruitment in the ABPM sub-study is closed in Amendment 4.]

12.13.3.1. ABPM Quality Control Criteria

Subjects will need to wear the ABPM device for two 24-hour sessions during the study: at Week -4 or at any time up until 1 week prior to randomization (baseline ABPM) and then at Week 16. The ABPM device will be placed after the assessments for the main study have been completed. Subjects will be expected to wear the ABPM device for 24 hours at each session. The ABPM device will measure BP and heart rate every 30 minutes during both awake and asleep hours. The times the subject awakens and goes to sleep during this 24-hour period will be recorded.

For each session, the ABPM Quality Control (QC) criteria as defined in the Project Requirement Specification (PRS) for ABPM must be met. If these criteria are not met the ABPM may be repeated (see Section 12.13.3.3).

12.13.3.2. Eligibility Criteria - Screening

Additional Inclusion Criteria

In addition to meeting entry criteria for the main study, a subject will be eligible for inclusion in this sub-study only if all of the following criteria apply.

- Signed written informed consent prior to beginning sub-study-related procedures.
Note: Consent to participate in this sub-study is separate from consent to participate in the main study, and will be signed either at Week -8 or at Week -4 prior to ABPM assessments.

2. Use of the same antihypertensive class treatment, including equivalent dose and category, (including diuretics) for the 6 weeks prior to the Screening visit, through the entire Screening period and at randomization.
3. SBP of ≤ 170 mmHg based on the average of clinic values obtained at Week -8 and Week -4 using the methodology described in the SRM.
4. Not using ESA's as defined in Section 5.1.
5. Willing and able to wear ABPM device for 24 hours on two separate sessions and to collect their urine during these same two separate 24 hour sessions.
6. Valid ABPM at baseline [**randomization (Day 1) only**].
7. Average awake-time SBP of ≤ 150 mmHg as assessed by a valid baseline ABPM [**randomization (Day 1) only**].

Additional Exclusion Criteria

A subject will not be eligible for inclusion in this sub-study if any of the following criteria apply:

1. Evidence of atrial fibrillation or atrial flutter at the time of baseline ABPM assessment (see Section 12.13.3.3).
2. Subjects who are at high risk for loss to follow-up (e.g., subjects who may require frequent hospitalizations).
3. Oscillometer/sphygmomanometer cuff cannot accommodate their upper arm circumference.
4. BP cannot be measured in the arm opposite of current vascular access.

12.13.3.3. Study Assessments

Week -8 Study Visit:

Subject's consent for ABPM is obtained (Note: if missed this may be obtained at Week -4 prior to ABPM assessments).

Week -4 Study Visit:

A baseline ABPM reading and the collection of a 24 hour urine sample will be initiated at the Week-4 visit but may be performed at a subsequent clinic visit provided it occurs at least 1 week prior to randomization.

Prior to ABPM, subjects will be assessed for the presence of atrial fibrillation/flutter as follows: subjects with an irregular heart beat detected during heart rate measurement will undergo an ECG and those with documented atrial fibrillation or atrial flutter will not be eligible for ABPM.

The ABPM device is attached by site personnel and will be removed by site personnel after 24 hours of wear (see SRM for guidance on attachment of ABPM device) when the subject returns the next day.

The subject will also collect their urine over 24 hours in a urine collection jug that will be issued at the visit, the subject will return their 24 hour urine sample the next day. This urine sample will be assessed for sodium, aldosterone and creatinine. It is recommended that the subject maintains their prescribed dietary intake of sodium during urine collection (see SRM for guidance on collection of urine).

If the subject fails to meet the baseline ABPM QC criteria and agrees to repeat the ABPM procedure, then:

- The baseline ABPM procedure can be repeated. *Note: the atrial fibrillation/flutter assessment should be repeated prior to device placement.*
- Day 1 (randomization) may be delayed.
- If the baseline ABPM fails the QC criteria after three attempts, then the subject will not be enrolled in this ABPM sub-study.

Day 1 (Randomization):

If the ABPM measurements meet the QC criteria the subject can be randomized.

Subjects who either do not qualify for entry into the ABPM sub-study after failing QC criteria a third time or who do not desire to continue in the ABPM sub-study although they pass the QC criteria, should continue with randomization into the main study following the schedule of assessments as outlined in [Table 7](#) of the main protocol if appropriate.

Week 16 Study Visit:

At Week 16, after all main study assessments have been completed, the ABPM device will be placed on the subject's arm by site personnel and the subject will wear the device for 24 hours until it is removed by site personnel the next day. The time of administration of study medication, before and while wearing the ABPM device, will be recorded. The subject will also be issued a urine collection jug during this clinic visit in which they will collect their urine over 24 hours and return it the next day when the ABPM device is removed (for subjects transitioning to dialysis, 24 hour urine collection to be done as able). It is recommended that the subject maintains their prescribed dietary intake of sodium during urine collection.

If the ABPM fails the QC criteria (same as baseline), up to two additional attempts may be made. No further attempts are allowed. The subject will continue study visits in the main study as scheduled.

12.13.3.4. Permanent Discontinuation of Randomized Treatment

A subject who permanently discontinues randomized treatment prior to completing the ABPM sub-study should remain in the sub-study and complete the Week 16 ABPM and 24 hour urine collection assessments unless consent to participate in the ABPM sub-study is withdrawn (see also Section 5.5).

12.13.3.5. Antihypertensive Medication Changes

It is preferred that no changes are made to antihypertensive medications while the subject is part of the sub-study.

If changes in antihypertensive medications are necessary, these must be documented in the eCRF along with the reasons. Subjects will remain in the sub-study regardless of any change.

12.13.3.6. Withdrawal from ABPM Sub-Study

If a subject participating in this sub-study withdraws from the sub-study, the reason for the withdrawal must be recorded in the eCRF. The subject will remain in the main study unless the subject withdraws consent from the main study.

12.13.4. Sample Size and Power Calculations

The sample size of this sub-study has been designed based on the primary sub-study objective to demonstrate superiority in average SBP change from baseline to end of sub-study between arms (daprodustat versus darbepoetin alfa), measured by ABPM over a 24 hour assessment period. Assuming a one-sided 2.5% significance level, a true standard deviation for SBP change from baseline measured by ABPM of 11 mmHg [Peixoto, 2000], and up to a 20% withdrawal rate from the sub-study, a sample size of 68 subjects per group (136 subjects in total) will provide greater than 80% power to detect a -6 mmHg difference in treatment groups (i.e., achieve superiority). Given the planned sample size, superiority will be established if there is more than a 4.2 mmHg mean difference observed in favor of daprodustat.

Assuming a 40% screen failure rate for the additional ABPM entry criteria, approximately 228 subjects that are eligible for the main study will need to be screened for the sub-study in order to randomize approximately 136 subjects. See Section 9.2.3 for more information about sample size adjustments.

Unblinded ABPM data will be reviewed by the IDMC during the conduct of the trial as part of their data monitoring responsibilities. No interim analysis is planned.

12.13.5. Statistical Analysis

The primary sub-study estimand is to compare the treatment effect on change from baseline in 24 hour average SBP at end of sub-study, in all randomized sub-study subjects. The statistical model for analysis will be an ANCOVA with terms for treatment and baseline 24 hour average SBP. This model will provide a point estimate and two-sided 95% CI for the treatment effect and a one-sided p-value for the superiority

assessment. Superiority will be established if the p-value is <0.025 . The primary analysis population will be the ABPM sub-study-ITT population defined as randomized subjects who were also entered into the ABPM sub-study.

Given the nature of ABPM measurement, a high degree of dropout unrelated to randomized treatment is anticipated. The potential high level of missing data poses a challenge in the interpretation of the primary ABPM sub-study analysis. The reason for missing ABPM data will be examined to explore the impact of missing data on the sub-study primary efficacy conclusions. If the majority (defined as $\geq 70\%$) of the missing data is due to either subject unwillingness to repeat the ABPM procedure or due to an unevaluable reading, then data will be treated as missing at random and the primary analysis will be considered sufficient. Otherwise, a sensitivity analysis may be performed that will use multiple imputation from the active control arm to replace data from both treatment groups that was missing due to reasons other than subject unwillingness or unevaluable readings. Further supplementary analyses may include an ABPM per-protocol population (PP) analysis, utilizing all ABPM-ITT subjects who are not major protocol violators or who did not change BP medications during the sub-study. Further details of sensitivity and supplementary analyses will be described in the RAP.

In order to contextualise the primary between-group comparison, a key secondary objective is to assess within-group changes from baseline over the sub-study. Assessment of within-group changes will support interpretation of the primary analysis by identifying whether there was an absence of an increase in BP in one or both treatment groups. To that end, two-sided 95% confidence intervals will be calculated for change from baseline in each ABPM parameter separately for each treatment group. For either treatment group, a lack of adverse effect on the primary endpoint of average SBP at end of sub-study will be concluded if the upper 95% confidence limit is no more than 4 mmHg. This margin was chosen as it is less than the clinically meaningful change of 5 mmHg [Whelton, 2002] and it is half the historical increase in SBP observed with rhEPO [Krapf, 2009].

The mean and two-sided 95% CI will be estimated from the primary statistical model for within treatment arm SBP change from baseline to end of sub-study.

The change from baseline 24 hour average DBP, mean arterial pressure and heart rate at end of sub-study will be assessed in a similar way, as the primary using analogous ANCOVA models with treatment and baseline as covariates.

The differences in proportion of subjects that increase/decrease their BP medication (number or dose) will be assessed using Fisher's Exact Test. The differences between treatment groups in the proportion of subjects that convert from dippers/ non-dippers at baseline to non-dippers/ dippers at end of sub-study will also be assessed using Fisher's Exact Test.

Plots of the mean 24 hour average values (two-sided 95% CIs) and mean changes from baseline in 24 hour average values (two-sided 95% CIs) for BP will be provided by treatment group.

Changes from baseline in 24 hour urine sodium excretion and 24-hour urine aldosterone excretion at end of sub-study will be analyzed in a similar manner to the primary ABPM endpoint, except that the statistical model for analysis will be an ANCOVA with terms for treatment and baseline 24 hour urine parameter.

Additional statistical considerations will be addressed in the RAP.

References

Agarwal RJ. Blood Pressure and Mortality Among Hemodialysis Patients. *Hypertension*. 2010; 55:762-768.

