1. PROTOCOL SYNOPSIS FOR STUDY 200808

This Phase 3 study will evaluate the safety and efficacy of daprodustat (GSK1278863) compared to the recombinant human erythropoietin (rhEPO), darbepoetin alfa, in the treatment of anemia associated with chronic kidney disease (CKD) in non-dialysis (ND) subjects.

Primary Objective(s)/Endpoint(s)

Objectives	Endpoints
Co-primary (tested in parallel for non-inferiority)	

 To compare daprodustat to darbepoetin alfa for cardiovascular (CV) safety (non-inferiority) 	
 Time to first occurrence of adjudicated major adverse cardiovascular event (MACE) [composite of all-cause mortality, non-fatal myocardial infarction (MI) and non-fatal stroke]

 To compare daprodustat to darbepoetin alfa for hemoglobin (Hgb) efficacy (non-inferiority) 	
 Mean change in Hgb between baseline and evaluation period (EP, mean over Weeks 28 to 52)

Overall Design

- This is a randomized, open-label (sponsor blind), active-controlled, parallel-group, multi-center, event-driven study in ND subjects with anemia associated with CKD.
- This study will comprise four study periods: a 4-week screening period, a 4-week placebo run-in period, a treatment period, and a follow-up period. Prior erythropoiesis-stimulating agents (ESA¹) therapy, if present, continues during the screening and run-in periods.
- The total duration of the study is dependent upon the accumulation of 664 adjudicated first MACE (i.e., it is event-driven) unless review of interim data by the Independent Data Monitoring Committee (IDMC) recommends bringing the study to an earlier close.
- Subjects will be stratified by region, by whether they are currently using an ESA, and by participation in the ambulatory blood pressure monitoring (ABPM) sub-study.
- Following stratification, subjects will be randomized 1:1 to receive oral daprodustat or subcutaneous (SC) darbepoetin alfa.
- Both treatment arms (daprodustat and darbepoetin alfa) will follow a protocol-specified randomized treatment dose adjustment algorithm to achieve and/or maintain Hgb within the target range of 10-11 g/dL. Dose changes will be made programmatically by the Interactive Response Technology (IRT) system for both randomized treatment arms.

¹ ESAs refer to any rhEPO or methoxy PEG-epoetin beta.

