- To ensure subjects remain iron replete and to minimize the potential for iron overload during the study, the investigator will follow the iron management criteria from randomization through the end of the study treatment period.
- A rescue algorithm is provided to minimize subjects having an inadequate response to the treatment for their anemia for an extended period of time and to enable consistency in the application of rescue therapy across the study.
- GSK will provide randomized treatment: daprodustat or darbepoetin alfa.

Type and Number of Subjects

This study will randomize approximately 4500 subjects (2250 subjects per treatment arm) with anemia associated with CKD not on dialysis and will enroll two groups of subjects:

- Group 1 (not using ESAs): subjects not currently receiving ESAs with a baseline HemoCue Hgb 8-10 g/dL.
- Group 2 (ESA users): subjects currently receiving ESA with a baseline HemoCue Hgb 8-11 g/dL.

The proportion of subjects not using ESAs (Group 1) and ESA users (Group 2) randomized into the study is expected to be approximately 60% and 40%, respectively.

Analysis

The study's co-primary endpoints will each be tested for non-inferiority using a one-sided 2.5% significance level and the relevant confidence bound from a two-sided 95% confidence interval (CI) (upper bound for MACE and lower bound for the Hgb co-primary endpoint).

For CV safety, the primary question is whether daprodustat is non-inferior to darbepoetin alfa for adjudicated MACE. An Intent-to-Treat (ITT) analysis of time to the first occurrence of adjudicated MACE using a margin of 1.25 and a Cox Proportional Hazards regression model, including factors for treatment and the prognostic randomization stratification factors (region and current ESA use), will be used.

For Hgb efficacy, the primary question is whether daprodustat is non-inferior to darbepoetin alfa for change from baseline in Hgb. The analysis will be based on the mean change in central laboratory Hgb between baseline and the efficacy EP (defined as mean over Weeks 28 to 52) using a non-inferiority margin of -0.75 g/dL. An analysis of the ITT Population and an analysis of covariance (ANCOVA) model will be used. The model will include prognostic randomization stratification factors (region and current ESA use), and factors for baseline Hgb and treatment.

Non-inferiority needs to be met for both co-primary endpoints for the study to be considered successful.

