4. STUDY DESIGN

4.1. Overall Design

[figure not shown]
- This is a randomized, open-label (sponsor blind), active-controlled, parallel-group, multi-center, event-driven study in ND subjects with anemia associated with CKD.
- This study will comprise four study periods ([Figure 1](#)): a 4-week screening period, a 4-week placebo run-in period, a treatment period, and a follow-up period. Prior ESA² therapy, if present, continues during the screening and run-in periods.
- The treatment period consists of ([Figure 1](#)):
 - The stabilization period, defined as the period from Day 1 to Week 28 during which randomized treatment will be dose titrated to achieve the appropriate Hgb target.
 - The maintenance period, defined as the period from the end of the stabilization period (Week 28) to the end of treatment (variable per subject), to assess long term safety and efficacy.
 - The efficacy evaluation period (EP) is defined as the period from Week 28 to Week 52 during which Hgb efficacy will primarily be assessed.
- The total duration of the study is dependent upon the accumulation of 664 adjudicated first MACE (i.e., it is event-driven) unless review of interim data by the Independent Data Monitoring Committee (IDMC) recommends bringing the study to an earlier close.
- All subjects will remain in the study (including subjects that start dialysis or receive a kidney transplant), regardless of whether they continue with randomized treatment (unless consent for any further follow up is withdrawn), until the target number of first adjudicated MACE has occurred. At that point, the sponsor will notify investigators to have subjects come in for an End of Study visit within a pre-defined time period.
- The end of the study will occur after the accumulation of 664 adjudicated first MACE and the last subject has completed their last required study visit ([Section 7.1](#)).
- Subjects will be stratified by region (see [Appendix 3](#)), by whether they are currently using an ESA, and by participation in the ABPM sub-study. Region and ESA use at study entry are stratification factors considered to be potentially prognostically important, i.e., predictive of study endpoints while participation in the ABPM sub-study is an administrative stratification factor intended solely to ensure a similar number of sub-study subjects in each of the two randomized groups. [Note: recruitment in the ABPM sub-study is closed in Amendment 4.]

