- Following stratification, subjects will be randomized 1:1 to receive oral daprodustat or SC darbepoetin alfa. A central randomization approach will be used to protect

² ESAs refer to any rhEPO or methoxy PEG-epoetin beta.

against potential selection bias due to the open-label design. The sponsor is blinded to treatment assignment in the main study and ABPM sub-study.

- Both treatment arms (daprodustat and darbepoetin alfa) will follow a protocol-specified randomized treatment dose adjustment algorithm to achieve and/or maintain Hgb within the target range of 10-11 g/dL (Section 6.3.3). Dose changes will be made programmatically by the IRT system for both randomized treatment arms.
- To ensure subjects remain iron replete and to minimize the potential for iron overload during the study, the investigator will follow the iron management criteria (Section 6.11.1) from randomization through the end of the study treatment period.
- A rescue algorithm is provided to minimize subjects having an inadequate response to the treatment for their anemia for an extended period of time and to enable consistency in the application of rescue therapy across the study (Section 6.12).
- An overview of the study design is provided in Figure 1.

Figure 1 Study Schematic

- This study will include the following sub-studies:
 - ABPM sub-study (subjects not using ESAs only) (Appendix 13) [Note: recruitment in the ABPM sub-study is closed in Amendment 4]
 - Pharmacokinetic (PK) sub-study (Appendix 14)
- An external independent Clinical Events Committee will conduct blinded adjudication of all events reported during this study that may meet the definition of the co-primary safety endpoint of MACE and additional endpoints as outlined in Section 7.4.1 and Section 10.8.2.
- An external IDMC will monitor the safety and efficacy data from the study (Section 10.8.1).

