9.4.1.2. Primary Efficacy Analysis (co-primary)

Mean change in Hgb between baseline and the EP (Weeks 28 to 52): The primary efficacy estimand is the effect of daprodustat relative to darbepoetin alfa on the change in Hgb from baseline to the average of all values in the EP, regardless of adherence to treatment including interruptions and discontinuation, the use of non-randomized ESA medication for any reason including rescue therapy, or the use of blood transfusions, in subjects not on dialysis with anemia secondary to CKD and assuming subjects do not die before the end of the EP. The analysis will use an analysis of covariance (ANCOVA) model. For each subject, baseline Hgb will be the value obtained on Day 1, prior to taking randomized treatment, and Hgb during EP will be determined by calculating the mean of all available and imputed Hgb values between Weeks 28 to 52 inclusive regardless of adherence to randomized treatment. The ANCOVA model will include prognostic randomization stratification factors (region and current ESA use), baseline hemoglobin and treatment. It will provide a point estimate and two-sided 95% CI for the treatment effect together with the one-sided non-inferiority test p-value. Non-inferiority will be established if the lower limit of the two-sided 95% CI is greater than the margin of -0.75 g/dL. Imputation will be used for missing Hgb data; further details will be provided in the RAP.

Sensitivity and Supportive Analyses: Sensitivity analyses for the primary estimand will include a multiple imputation-based “tipping point” analysis where assumptions are adjusted until non-inferiority is lost by imputing data for subjects who did not fully complete the EP. A supportive analysis will evaluate efficacy in those subjects who adhere to randomized treatment, defined as subjects with at least one on-treatment Hgb during the EP (this approach corresponds to evaluating an efficacy estimand). A supportive “tipping point” analysis as that described above for the primary analysis will be performed for this “on-drug” analysis. In addition, a per-protocol supportive analysis will estimate the treatment effect in subjects who strongly adhere to the protocol, and supportive analyses to explore a shorter EP (Weeks 28 to 36) will be performed for the co-primary effectiveness estimand and “on-drug” efficacy estimand. Full details of all sensitivity and supportive analyses will be provided in the RAP.

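### The ABPM sub-study ANCOVAs omit region, the only randomization stratum that varies within the sub-study, so the test is valid but possibly conservative

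*Protocol*

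**What the plan says.** Section 12.13.5 gives the primary sub-study model in full: "The statistical model for analysis will be an ANCOVA with terms for treatment and baseline 24 hour average SBP". It then applies analogous models, with treatment and the matching baseline, to 24-hour diastolic pressure, mean arterial pressure, heart rate, and urinary sodium and aldosterone.

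The synopsis describes the randomization: "Subjects will be stratified by region, by whether they are currently using an ESA", and by ABPM participation. Section 4.1 says of these factors: "Region and ESA use at study entry are stratification factors considered to be potentially prognostically important, i.e., predictive of study endpoints". It treats ABPM participation as purely administrative.

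The main-study models act on that view. For hemoglobin, Section 9.4.1.2 says: "The ANCOVA model will include prognostic randomization stratification factors (region and current ESA use), baseline hemoglobin and treatment". The Cox model for MACE in Sections 9.1.1 and 9.4.1.1 adjusts for the same two factors.

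Sub-study entry requires (Section 12.13.3.2): "Not using ESA's as defined in Section 5.1".

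**The concern.** Every sub-study subject is an ABPM participant and a non-user of ESAs, so two of the three strata are constant. Region is the only one left, and the sub-study model leaves it out with no reason given. The protocol thus does not carry its own rationale for adjustment into the sub-study.

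Stratified randomization balances region across the arms. If region predicts the outcome, that balance reduces the true variance of the treatment difference. A model without region leaves the between-region variance in its residual and does not credit the reduction. The confidence interval is then wider than it need be, and the one-sided test runs below its nominal 2.5%. What is at stake is efficiency and consistency with the main analyses, not bias.

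**Working it through.** **Inputs from Section 12.13.4.** 68 subjects per arm, up to 20% withdrawal, SD of change 11 mmHg, difference 6 mmHg, one-sided 2.5%. Evaluable per arm: 68 × 0.8 = 54.4, taken as 54. Allocation is 1:1 (Section 4.1). Appendix 3 lists five regions. The sub-study runs in selected countries, and the number of regions contributing is not stated.

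**The plan's own figures, without region.**
- SE = 11 × √(2/54) = 2.117 mmHg.
- Smallest significant observed difference = t(0.975; 106 df) × SE = 1.983 × 2.117 = 4.20 mmHg. The plan states 4.2.
- Noncentrality = 6/2.117 = 2.834. Power is 80.2% by noncentral t and 80.9% by the normal approximation. The plan states more than 80%.

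Both stated figures reproduce, and neither relies on adjusting for region.

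**Effect of region.** Let R² be the share of residual variance, after baseline, that region explains. The documents give no value, so a range is assumed. The total SD is held at 11, with balance within region.
- SE reported without region: 2.117.
- True SE, and SE with region in the model: 2.117 × √(1 − R²).
- Power without region: Φ[(6 − 1.983 × 2.117) / true SE].
- Power with region: noncentral t with 108 − 3 − 4 = 101 df and noncentrality 6 / true SE.

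Example at R² = 10%: true SE = 2.117 × √0.90 = 2.008. Power without region is Φ[(6 − 4.198)/2.008] = Φ(0.897) = 81.5%. With region it is 84.1%.

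| Assumed R² | True SE | Reported SE too large by | Power without region | Power with region | Gain (points) |
|---|---|---|---|---|---|
| 0 | 2.117 | 0% | 80.3% | 80.2% | −0.1 |
| 2% | 2.096 | 1.0% | 80.5% | 80.9% | +0.4 |
| 5% | 2.063 | 2.6% | 80.9% | 82.1% | +1.2 |
| 10% | 2.008 | 5.4% | 81.5% | 84.1% | +2.6 |
| 20% | 1.893 | 11.8% | 82.9% | 88.1% | +5.2 |

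**Simulation check.** The set-up was permuted blocks of 4 in five regions and 108 subjects, with 6,000 runs per power value and 12,000 per type I error value. The gains were −0.3, +0.4, +1.4, +2.8 and +5.8 points in the order of the table. Type I error without region was 2.47, 2.53, 2.33, 1.87 and 1.36%. The simulation standard error is about √(0.025 × 0.975/12,000) = 0.14 points, so type I error is at or below 2.5% throughout.

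**If baseline pressure also explains variance.** The SD of 11 is for raw change. If baseline explains an assumed 25% of it, the SE without region is 11 × √0.75 × √(2/54) = 1.833. At R² = 10%, power is then 91.3% without region and 92.7% with it.

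**The case against.** The case for leaving the model alone has five parts.

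- **Nothing shows that region predicts change in ambulatory systolic pressure.** Section 4.1 says only that it is potentially prognostic for study endpoints in general. Sub-study entry also requires stable antihypertensive treatment and awake systolic pressure of at most 150 mmHg, which may narrow regional differences. This stands. A reader might infer that the standard error is overstated and power is lost as a matter of fact, but the documents do not support that. At R² = 0 there is no loss.
- **The stated power is met without region.** This also stands. A reader might infer that the sub-study is underpowered or has no margin to give up. In every scenario above, power without region exceeds 80%, and the planned baseline adjustment may add power that the sample size did not count.
- **The analysis is valid.** The estimate is unbiased, and type I error departs only in the safe direction. This stands.
- **It is late to change.** Recruitment to the sub-study closed in Amendment 4, dated 16 August 2019, and the endpoint is at Week 16 (Week 28 for subjects who completed earlier). Readings had probably been collected by Amendment 5 of 30 July 2020. But the sponsor is blinded to sub-study assignment (Section 6.4), so the model can still be changed without knowledge of the results.
- **Five regions among about 108 evaluable subjects may be sparse, and withdrawal can disturb the balance.** This is fair. It calls for a pooling rule and makes the gains approximate.

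These points make the matter smaller. They do not supply a reason for omitting region. Section 12.13.5 leaves additional considerations to the RAP, but it fixes the primary model itself.

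**Conclusion.** This is a minor point of efficiency and consistency. The sub-study models omit the one randomization stratum that varies within the sub-study, although the protocol adjusts both co-primary models for it. The planned test is valid and its stated power holds. Whether it is conservative depends on how much residual variance region explains, which the documents do not give. For an assumed 0 to 10%, adding region changes power by about −0.1 to +2.6 points, with 54 evaluable per arm, SD 11 mmHg, a 6 mmHg difference and balance within region. The possible loss is negligible and the possible gain modest, which favors adjusting. The power figures concern the primary systolic endpoint only. For the secondary and exploratory models the argument is consistency.

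**What to change.** Before unblinding, add region as a fixed factor to the ABPM systolic ANCOVA in Section 12.13.5 and to the analogous diastolic, mean arterial pressure, heart rate and urine models. Use the Appendix 3 groupings, and pool sparse regions by a rule set on blinded data. The within-arm means judged against 4 mmHg come from the same primary model, so also state how regions are weighted in those means.

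The cost is a short amendment to the protocol or RAP, the pooling rule, and up to 4 degrees of freedom, worth about 0.1 point of power if region explains nothing. No new data are needed.
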